2. OVERVIEW (SYNOPSIS)

Sponsor: PROMOMED RUS LLC, Russia	Separate study table relating to part of the dossier	(For use by national authorized bodies only)
Name of finished product: Areplivir, film-coated tablets	Volume: Pages:	
Active ingredient: Favipiravir		
Protocol No.: FAV052020		
Clinical study name: Open randomized multicenter comparative study on the efficacy and safety of Areplivir film-coated tablets (PROMOMED RUS LLC, Russia) in patients hospitalized with COVID-19		
Investigators, Study site: The study is conducted at five research centers in the Russian Federation. Detailed information is provided in Section 6.		
Publication: A list of scientific papers and publications relevant to this study will be presented in the Clinical Study Final Report.		
Study period: Q2 2020 – Q4 2020	Drug development phase: III	
Study purpose: Assess the efficacy and safety of Areplivir versus standard therapy in patients hospitalized with COVID-19. Study objectives: 
 • Assess the efficacy of Areplivir versus standard therapy in patients hospitalized with COVID-19. • Assess the safety of Areplivir versus standard therapy in patients hospitalized with COVID-19. 		
Methodology: an open randomized multicenter comparative study on the efficacy and safety of Areplivir in patients hospitalized with COVID-19.		
Number of patients (planned and included in the analysis): The study will randomize 200 patients. Given the possible non-inclusion of patients at the screening stage, the maximum number of patients to sign the Informed Consent Form in the Patient Information Leaflet and to participate in screening can be no more than 210 people. This interim report is based on data on 80 patients (40 patients in the Areplivir arm + 40 patients in the standard therapy arm). Patients who met the inclusion criteria and did not meet the non-inclusion criteria were randomized to 2 groups (treatment arms) in a 1:1 ratio: Arm 1 (n=100) receives the study drug Areplivir film-coated tablets: on day 1 of therapy - 1600 mg (8 tablets) 2 times a day; on days 2-14 of treatment - 600 mg (3 tablets) 2 times a day. The drug is taken orally every 12 hours, swallowing whole tablet without chewing and washing down with a glass of water. The course of treatment is 14 days.		

Sponsor: PROMOMED RUS LLC, Russia	Separate study table relating to part of the dossier	(For use by national authorized bodies only)

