
Diagnosis and key inclusion criteria:
 
The study is conducted with the participation of male and female patients aged 18 to 80 years inclusive, hospitalized with COVID-19.
 
Inclusion criteria:
 
 1. Signing and dating of the Informed Consent Form of the Patient Information Leaflet (PIL) by patients. 2. Men and women aged 18 to 80 years inclusive at the time of signing the Informed Consent Form in PIL. 3. No difficulty with oral medication (e.g. swallowing disorder). 4. Patient diagnosed with "Coronavirus infection caused by SARS-CoV-2 (confirmed)¹, medium severity form*" established in accordance with the Interim Guidelines of the Russian Ministry of Health for the prevention, diagnosis and treatment of a new coronavirus infection (COVID-19), (revision 6 of 28.04.2020). *Medium severity form: fever above 38 °C, BR above 22/min, dyspnea during exercise, pneumonia (confirmed by lung CT), SpO2 < 95%, CRP serum level above 10 mg/l. 5. Patient should be hospitalized no more than 48 hours before the start of the study therapy. 6. Positive PCR result for presence of SARS-CoV-2 RNA at screening phase (results obtained within 7 days prior to screening are appropriate). 7. Patient's consent to use reliable contraceptive methods throughout the study and within 1 month for women and 3 months for men after its completion. Persons eligible for participation in the study: 
 – Women who have a negative pregnancy test and use the following contraceptives: barrier method (condom or occlusive cap (diaphragm or cervical/vaulted cap)) or double barrier method of contraception (condom or occlusive cap (diaphragm or cervical/vaulted cap) plus spermicide (foam/gel/film/cream/suppository)). Women incapable of childbearing may also participate in the study 		

¹ Positive PCR result for SARS-CoV-2 RNA.

Sponsor: PROMOMED RUS LLC, Russia	Separate study table relating to part of the dossier	(For use by national authorized bodies only)
Name of finished product: Areplivir, film-coated tablets	Volume: Pages:	
Active ingredient: Favipiravir		

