Sponsor: PROMOMED RUS LLC, Russia	Separate study table relating to part of the dossier	(For use by national authorized bodies only)
Name of finished product: Areplivir, film-coated tablets	Volume: Pages:	
Active ingredient: Favipiravir		
Investigational medicinal product, dose and mode of administration, batch number: Investigational medicinal product: Areplivir, film coated tablets (PROMOMED RUS LLC, Russia), batch 010520 (expiry date 06.2022). Patients in Arm 1 take the investigational product Areplivir, film coated tablets: on Day 1st of treatment - 1600 mg (8 tablets) 2 times a day; on days 2-14 of treatment - 600 mg (3 tablets) 2 times a day. The drug is taken orally every 12 hours, swallowing whole tablet without chewing and washing down with a glass of water. The course of treatment is 14 days. The test drug is administered in hospital setting under supervision of a clinical investigator. The test drug is not handed over to the patient.		
Duration of the study: The total duration of the study for the patient is not more than 31 days, of which the screening period is not more than 2 days. Visits: Visit 0 (screening, not more than 2 days); Visit 1 (randomization, day 1)*; Visit 2 (day 5); Visit 3 (day 10); Visit 4 (day 15)**; Visit 5 (day 21±1)***; Visit 6 (study completion, day 28±1)***. * Visit 1 may coincide with Visit 0. ** If a patient is discharged from hospital at an earlier date, the visit will be conducted at the time of discharge (for Arm 2 patients). *** If a patient is discharged from hospital at an earlier date, then this patient does not need to visit the study site. Fatalities and serious adverse events (SAE) will be followed-up through telephone contact with the patient. Discharge of patients from a hospital is carried out in accordance with the local practice of the study site in compliance with the current sanitary and epidemiological regime.		
Efficacy criteria: The efficacy of therapy is assessed using the following endpoints: Primary efficacy criterion: 
 • Time (in days) to improvement in clinical status by categorical ordinal scale of clinical status improvement. • Rate of clinical status improvement by categorical ordinal scale of clinical status improvement by 2 or more categories at Visit 3. Secondary efficacy criteria:		

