
Sponsor: PROMOMED RUS LLC, Russia	Separate study table relating to part of the dossier	(For use by national authorized bodies only)
Name of finished product: Areplivir, film-coated tablets	Volume: Pages:	
Active ingredient: Favipiravir		

The proof of the superiority hypothesis is the establishment of a statistically significant time difference (in days) before patient's clinical status improvement between the Areplivir arm and the standard therapy arm.

The next primary efficacy parameter is the percentage of patients who achieved an improvement in clinical status according to the categorical ordinal scale of clinical improvement by 2 or more categories at Visit 3.

- Rate of clinical status improvement by categorical ordinal scale of clinical status improvement by 2 or more categories at Visit 3.

For the analysis of this parameter, an intergroup comparison of percentages is used using a two-sided version of the **Fischer's exact test** (or a two-sided version of the χ^2 (chi-square) test, if all the expected values in the cells of the contingency table for this analysis are 5 or more). The percentage of patients who achieved improvement in clinical status on a categorical ordinal clinical improvement scale by 2 or more categories at Visit 3 is presented with a two-sided 95% confidence interval by treatment arm. Hypothesis testing is performed at a 5% significance level. The difference in proportion between treatment arms and the 95% bilateral confidence interval for the difference in proportion calculated by **Newcomb-Wilson technique is presented**.

The proof of the hypothesis of superiority of Areplivir film-coated tablets (PROMOMED RUS LLC, Russia) is the establishment of a statistically significant difference in the proportions of patients who achieved an improvement in clinical status according to the categorical ordinal scale of clinical improvement by 2 or more categories at Visit 3, between Areplivir arm and standard therapy arm.

Analysis of the primary efficacy parameter is performed in the ITT population (main analysis), and in the PP population (additional analysis). A summary of all efficacy indicators is provided.

Analysis of secondary efficacy parameters

The following efficacy parameters in the protocol are represented by qualitative values:

- Percentage of patients with elimination * COVID-19 according to PCR analysis at Visit 3.
- Percentage of patients transferred to intensive care unit.

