- Percentage of cases with non-invasive lung ventilation.
- Percentage of cases with mechanical lung ventilation.
- Incidence of fatal cases.
- Assessment of lung injury according to CT data at Visits 4, 5 and 6.**

* Virus elimination is defined as two negative laboratory tests for SARS-CoV-2 RNA obtained at intervals of 24 hours.

**An "empirical" visual scale will be used to estimate changes in lung involvement from CT data.

For the analysis of these parameters, an intergroup comparison of shares is used using a two-sided version of the **Fischer's exact test** (or a two-sided version of the χ^2 (chi-square) test, if all the expected values in the cells of the contingency table for this analysis are 5 or more).

The protocol also includes the following endpoint:

- Time (in days) to fever disappearance (body temperature < 37.2 ° C for 3 consecutive days

Sponsor: PROMOMED RUS LLC, Russia	Separate study table relating to part of the dossier	(For use by national authorized bodies only)
Name of finished product: Areplivir, film-coated tablets	Volume: Pages:	
Active ingredient: Favipiravir		

without antipyretic medication).

For the secondary efficacy parameter "time (in days) to fever disappearance (body temperature < 37.2 °C for 3 consecutive days without antipyretic drugs), a comparison between arms is made using the *Student's t-test* or the *Mann-Whitney test* (depending on the nature of the distribution of quantitative indicators). Also, *Kaplan-Meier technique* and the construction of *survival tables* can be used as descriptive methods of study. The *Gehan-Wilcoxon test, the Cox-Mentel test or the Log-Rank test* can be used to compare the time (in days) to the disappearance of fever in the study arms.

Analysis of secondary efficacy parameters is performed in the ITT population (main analysis), and in the PP population (additional analysis).

In case of developing acute respiratory distress syndrome and the need to switch patient to mechanical ventilation, the investigational drug is canceled, but the patient is not withdrawn from the study. Patients are under follow-up until Visit 6, the data are taken into account to assess efficacy in the ITT population.

Safety Analysis

Safety criteria

Safety assessment includes the following parameters:

- Total number of adverse events (AEs) stratified by severity and incidence;
- Incidence of adverse drug reactions;

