
Said statistical power (45%) is acceptable for exploratory stages of the studies aimed to select the duration for endpoint monitoring and to select the endpoint at the second (confirming) stage. In case change of the planned endpoints, separate adjustment will be made for the multiplicity of comparisons and the required number will be recalculated at the second stage.
 
Significance level used in the clinical study Significance levels and confidence intervals are calculated as bilateral, the statistical significance of differences is two-sided by default and refers to significance level 0.05 (unless specified otherwise).
 
Stopping criteria for the clinical study This protocol does not contain any statistical criteria for stopping the clinical study.
 
Accounting for missing data, data not to be analyzed and questionable data In the case of for missing data, data not to be analyzed and questionable data, appropriate statistical analysis methods are applied. Patients who will not be able to complete the course of therapy according to the protocol are included in the analysis of the main endpoint using the last observation carried forward (LOCF) method. This means that measures taken as criteria for efficacy will be assessed for such patients at the time of dropping out of the study.
 
Procedures for reporting any deviations from the original statistical plan All deviations from the final version of the statistical analysis plan will be described and substantiated in the final clinical study report.
 
Population analysis The statistical analysis includes the following patient populations:
 
 Safety population: patients who have received at least one dose of the study drug and for whom there is an assessment of condition and/or AE for at least one time point after administration. Population of all patients included in the study (Intent-to-treat, ITT): patients who received at least one dose of the drug in the study and for whom there is data for at least one visit after the baseline (Visit 0). Population of patients who completed the study as per the Protocol (Per protocol, PP): patients who have completed the study as per the Study Protocol. 
In case of developing acute respiratory distress syndrome and the need to switch patient to mechanical ventilation, the investigational drug is canceled, but the patient is not withdrawn
									

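### The main efficacy set is called ITT but is a modified ITT set, and the synopsis plans no analysis of all randomised patients

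*Combined protocol and SAP*

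**What the plan says.** All references are to the synopsis of the combined protocol and SAP.

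- **Name of the set** (Population analysis): "Population of all patients included in the study (Intent-to-treat, ITT").
- **Membership, in the same sentence:** "patients who received at least one dose of the drug in the study and for whom there is data for at least one visit" later than Visit 0, which is the baseline.
- **Use for the primary endpoints** (Analysis of primary efficacy parameter): "Analysis of the primary efficacy parameter is performed in the ITT population (main analysis), and in the PP population (additional analysis").
- **Use for the secondary endpoints** (Analysis of secondary efficacy parameters): "Analysis of secondary efficacy parameters is performed in the ITT population (main analysis), and in the PP population (additional analysis").
- **Design** (Methodology): "an open randomized multicenter comparative study on the efficacy and safety of Areplivir in patients hospitalized with COVID-19". Allocation is 1:1.
- **Visits** (Duration of the study): Visit 0 is screening, Visit 1 is randomisation on day 1, Visit 2 is day 5. A footnote adds that "Visit 1 may coincide with Visit 0". Another says that an Arm 2 patient who goes home early has Visit 4 at discharge.
- **Missing data:** patients who cannot finish the course enter the main endpoint analysis by last observation carried forward (LOCF).
- **Ventilated patients:** they stop the study drug, are followed to Visit 6, and remain in the ITT set.

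**The concern.** The name and the rule do not agree. Receiving a dose and having a later visit are both settled after randomisation, so a patient can be randomised and still fall outside the set. Readers will take ITT to mean that everyone randomised is analysed in the assigned arm, which is what protects the comparison from selection.

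Two features of the design make this more than a naming matter. First, both patient and investigator know the allocation, so declining treatment or leaving early may depend on the arm. Second, the dose condition speaks of one drug. Arm 1 has a defined product. Arm 2 has standard therapy, chosen by the investigator from guideline regimens according to what the site has available, and the synopsis does not say what counts as a dose there. The same sentence could therefore be applied differently in the two arms. Any resulting bias could go either way.

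**Working it through.** **1. Who can fall out of the set.** Taking each rule in turn:

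- *Never dosed.* The dose condition excludes them. Neither the LOCF rule nor the ventilation rule clearly brings them back.
- *Dosed, with Visit 1 held separately from Visit 0.* Visit 1 already counts as a visit after Visit 0, so the visit condition is met.
- *Dosed, with Visits 0 and 1 coinciding, then discharged early in Arm 2.* Visit 4 takes place at discharge, so the visit condition is met.
- *Dosed, with Visits 0 and 1 coinciding, then lost before day 5 for another reason.* There is no visit after Visit 0, so the definition excludes them. The LOCF text could be read as including them. The two statements are not reconciled.

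The patients at risk are therefore the first and last groups.

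**2. Whether another analysis covers them.** The per-protocol set requires completion according to the protocol. The safety set also requires a dose and a later assessment. No third efficacy set is defined.

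**3. Illustration of size.** The documents give no exclusion counts. The counts below are assumed, and so is the status of the excluded patients (all non-responders).

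Inputs from the synopsis: 100 per arm, two-sided 0.05, and response rates of 65% and 80% from the power tables. The sample-size text also mentions 70% on standard therapy. The test is the chi-square test, equivalent to

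z = (x1/n1 − x2/n2) / √[p̄(1 − p̄)(1/n1 + 1/n2)], with p̄ = (x1 + x2)/(n1 + n2).

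The plan gives no figure on this point. As a check on the method, exact binomial enumeration of the one-sided pooled test at 40 per arm, 65% against 80%, returns the plan's stated power of 0.4553.

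*Type I error* (same true rate in both arms, binomial probabilities summed over all outcomes with |z| at or beyond 1.96):

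| Non-responders dropped | 65% true rate | 70% true rate |
|---|---|---|
| none | 5.0% | 5.1% |
| 1 per arm | 5.2% | 5.4% |
| 1 from one arm | 5.3% | 5.3% |
| 3 per arm | 5.9% | 6.0% |
| 3 from one arm | 6.5% | 6.8% |

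The two-sided total hides the direction. At 65%, with three dropped from Areplivir only, the chance of a false finding in favour of Areplivir goes from 2.5% to 5.2%, and the chance of one in favour of control falls to 1.3%.

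*The plan's own scenario, 80/100 against 65/100:*

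- Nobody dropped: p̄ = 145/200 = 0.725; standard error √(0.725 × 0.275 × 0.02) = 0.0631; z = 0.15/0.0631 = 2.38; p = 0.018.
- Three dropped from Areplivir only: 80/97 − 65/100 = 17.5 points; p̄ = 145/197 = 0.736; standard error 0.0628; z = 2.78; p = 0.005.

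| Dropped | Difference (points) | p (chi-square) |
|---|---|---|
| none | 15.0 | 0.018 |
| 1 per arm | 15.2 | 0.016 |
| 3 per arm | 15.5 | 0.013 |
| 3 from Areplivir only | 17.5 | 0.005 |
| 3 from control only | 13.0 | 0.039 |

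The smallest expected cell count in these tables is 24.5, so the plan's rule selects chi-square over Fisher's exact test.

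**The case against.** The restriction is printed beside the name, so nobody who reads that sentence is misled, and the choice between ITT and modified ITT is partly a matter of labelling. Treatment is given in hospital, and an inclusion criterion reads "Patient should be hospitalized no more than 48 hours before the start of the study therapy", so undosed patients should be rare. Early-discharged controls keep a visit, and ventilated patients stay in. The LOCF sentence, read generously, already covers early losses. In the plan's own scenario the chi-square p-value stays below 0.05 under every assumed pattern above, and balanced losses move the difference by no more than half a point.

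Most of this stands, and it limits the severity. It does not remove the point: an undosed randomised patient is still excluded, nothing in the synopsis restores that patient, and the Arm 2 dose condition remains undefined.

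A reader might go further and infer any of the following. The documents do not support them.

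- *That patients have already been lost in this way.* The synopsis says "This interim report is based on data on 80 patients", 40 per arm, which equals the stage 1 plan. That shows no sign of loss, although the analysis set is not named.
- *That early discharge removes control patients.* The Visit 4 footnote prevents this.
- *That the result is biased towards Areplivir.* No exclusion counts are given, so neither size nor direction can be stated.
- *That an all-randomised analysis exists nowhere.* Only the synopsis is at hand, and it refers to a final SAP that may say more.

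**Conclusion.** The point holds, at low to moderate severity. The set called ITT is a modified ITT set, and the synopsis plans no efficacy analysis of all randomised patients. In an open-label trial with a dose condition that is unclear for one arm, this allows exclusions after randomisation that could differ by arm.

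The number affected is probably small. The illustration suggests little effect if losses are balanced, and a modest one if about three non-responders leave one arm only (type I error about 6.5% to 6.8% instead of 5%). Those figures rest entirely on assumed counts and assumed non-response. The finding about the definition does not depend on them.

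**What to change.** 1. Define ITT as all randomised patients, analysed in the arm assigned, and make it the main efficacy analysis.
2. For the Visit 3 responder endpoint, count patients with no post-baseline data as non-responders. Carrying Visit 0 status forward under the plan's LOCF rule gives the same answer, since no change cannot be an improvement of two categories.
3. Keep the present set as a sensitivity analysis called modified ITT. Word its dose condition for both arms: at least one dose of Areplivir in Arm 1, or of any standard-therapy drug received on or after randomisation in Arm 2. Include therapy begun earlier and continued, because patients may have been in hospital for up to 48 hours before study therapy, and controls already on treatment should not be excluded for that reason.
4. Report exclusions from each set by arm, with reasons.
5. State how patients without post-baseline data enter time to improvement, which is also primary, and the secondary endpoints (fever, PCR, CT and the event rates). These rules need separate choices, and none is proposed here.

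**Cost.** No extra patients or visits. The work is redefining one set, renaming another, writing the rules in item 5, and producing additional tables and an exclusion listing. Response rates may fall slightly, and counting missing patients as non-responders penalises the arm that loses more. The modified ITT analysis is kept so that readers can see how much this matters.

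### The per-protocol set keeps only study completers but is also used for deaths, intensive-care transfer and ventilation, so its mortality table is empty by construction; whether patients with cancelled drug stay in it is not settled

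*Combined protocol and SAP*

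**What the plan says.** All references are to the combined protocol and SAP, section 2, Overview (Synopsis).

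- **PP definition** (Population analysis): "patients who have completed the study as per the Study Protocol". Nothing further says what completion means or how a death is classified.
- **Completion point** (Duration of the study): "Visit 6 (study completion, day 28±1"). A patient discharged early need not attend the last two visits; deaths and serious adverse events are then followed by telephone.
- **Use of PP for secondary criteria** (Analysis of secondary efficacy parameters): "Analysis of secondary efficacy parameters is performed in the ITT population (main analysis), and in the PP population (additional analysis"). The criteria covered include "Incidence of fatal cases", "Percentage of cases with mechanical lung ventilation", "Percentage of cases with non-invasive lung ventilation" and transfer to intensive care.
- **Use of PP for the primary criteria** (Analysis of primary efficacy parameter): "Analysis of the primary efficacy parameter is performed in the ITT population (main analysis), and in the PP population (additional analysis").
- **Cancellation rule** (stated in the secondary-efficacy, safety and population parts): when ARDS develops and mechanical ventilation is needed, "the investigational drug is canceled, but the patient is not withdrawn from the study". Follow-up continues to Visit 6, and the data are said to count for efficacy in the ITT population. PP is not mentioned.
- **Arms**: only Arm 1 takes the investigational drug. Arm 2 receives standard therapy, and no matching cancellation rule is given for it.

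**The concern.** A completers-only set is conditioned on surviving to the end of follow-up. Using it to analyse death means using a set from which the event has already been removed. The same selection affects intensive-care transfer and ventilation, because the patients with the worst course are the ones most likely to die before Visit 6. Such tables would look reassuring and could not show harm. All-cause death is named only among the efficacy criteria: the safety criteria list no mortality item of their own, and the serious-event criterion is limited to events associated with treatment.

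The primary Visit 3 rate is measured at day 10, but PP membership depends on what happens up to day 28±1. A patient with a valid Visit 3 assessment who dies later is lost from the PP version. If such patients tend to be Visit 3 non-responders, the PP rate rises in both arms, and rises more in the arm with more deaths.

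The second issue is one of silence. The cancellation rule can be triggered only in Arm 1, and the plan does not say what it does to PP membership. In an open-label trial that question should be answered before outcomes are known, not by judgement afterwards.

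**Working it through.** The plan gives no figure for this point and no event rates, so there is nothing of its own to reproduce. The first step compares passages; the others use assumed counts with 100 patients per arm.

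**1. Deaths.** Membership in PP requires completing the study; completion is at Visit 6; a patient who dies before Visit 6 cannot reach it; no passage counts death as completion. If d patients per 100 die before Visit 6, the PP result is 0/(100 − d), which is 0% for any d. Example with assumed deaths of 10 and 2:

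- ITT: 10/100 vs 2/100, two-sided Fisher's exact p = 0.033.
- PP: 0/90 vs 0/98. The comparison is empty.

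**2. Ventilation among survivors only.** Assume 10 ventilated patients per arm, of whom 5 die, and no exclusion for drug cancellation. ITT gives 10/100 = 10%. PP gives (10 − 5)/(100 − 5) = 5/95 = 5.3% in each arm. About half the events disappear.

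**3. Visit 3 rate, later deaths removed.** Assume 70 responders per 100 in both arms, deaths of 10 and 2, all in Visit 3 non-responders. ITT: 70/100 vs 70/100, difference 0. PP: 70/90 = 77.78% vs 70/98 = 71.43%, difference 6.35 points, in favour of the arm with more deaths.

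**4. Cancellation rule, two readings.**

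- *Patient stays in PP.* The rule says the patient is not withdrawn and is followed to Visit 6. A surviving ventilated patient then completes the study in either arm, and no asymmetry arises.
- *Patient leaves PP.* The rule names only the ITT population for these data, and the patient has not received the 14-day course. The exclusion would then fall on Arm 1 only.

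Under the second reading, take v ventilated patients per arm, all Visit 3 non-responders, 70 responders per 100 in both arms, and no Arm 2 exclusions. The spurious difference is 70/(100 − v) − 70/100:

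| v | Arm 1 PP | Arm 2 PP | Difference |
|---|---|---|---|
| 3 | 70/97 = 72.2% | 70.0% | 2.2 points |
| 5 | 70/95 = 73.7% | 70.0% | 3.7 points |
| 8 | 70/92 = 76.1% | 70.0% | 6.1 points |

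These are upper bounds, because they keep every Arm 2 patient in PP, whereas step 1 shows that Arm 2 deaths leave it too. Removing m Arm 2 deaths gives 70/(100 − v) − 70/(100 − m):

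- v = 8, m = 4: 70/92 − 70/96 = 76.1% − 72.9% = 3.2 points.
- v = 5, m = 2: 70/95 − 70/98 = 73.7% − 71.4% = 2.3 points.

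On the same reading, the mechanical-ventilation criterion itself would be distorted: with the step 2 counts, PP becomes 0/90 vs 5/95 (p = 0.060) although the true rates are equal.

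**The case against.** **PP is only supportive.** ITT is declared the main analysis for primary and secondary criteria, ventilated patients are expressly kept in it to Visit 6, and deaths after early discharge are followed by telephone. No success criterion is set on PP, and the plan nowhere says that agreement between PP and ITT will be claimed as robustness. All of this stands. It limits the consequence to the additional analysis, but it does not make an empty mortality table or survivor-only ventilation tables worth producing.

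**The cancellation rule does not clearly exclude anyone.** A reader might infer that ventilated Areplivir patients are dropped from PP while ventilated control patients stay, so that PP is biased toward Areplivir. The documents do not support that as a finding. The PP definition speaks of completing the study, not the treatment course, and the plan separates the two: its missing-data rule refers to patients who cannot complete therapy. Cancellation is itself prescribed by the protocol, and the patient is followed to Visit 6. On the same Visit 6 reading that removes deaths, a surviving ventilated patient remains in PP in both arms. The only contrary sign is that ITT alone is named. What stands is an ambiguity that needs a rule. It concerns ARDS with mechanical ventilation only, not non-invasive ventilation or intensive-care transfer by themselves.

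**The population enrolled has moderate disease.** Patients who need intensive care at entry are excluded, so ventilation and death may be uncommon. That may make the numbers small; it does not alter the logic of step 1.

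**This is a synopsis.** It mentions a final statistical analysis plan, which may hold fuller PP rules. None is in the text reviewed, and the rule that is present gives the wrong result if followed as written.

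**Conclusion.** The point holds for deaths and for survivor selection. Followed as written, the PP mortality rate before Visit 6 is 0% in each arm for any treatment effect, PP rates of intensive-care transfer and ventilation describe survivors only, and the PP Visit 3 analysis loses patients because of later deaths. This rests on the plain meaning of completing the study and on no assumed rate.

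The effect of drug cancellation on PP membership is unresolved. Only if such patients were excluded would the exclusion be confined to Arm 1 and favour Areplivir. The 2.2 to 6.1 points for 3 to 8 ventilated patients per 100 are then an upper bound under assumed counts, 70% response in both arms and no Arm 2 deaths. They are not an estimate of bias in this trial; the largest falls to 3.2 points if 4 of 8 die in each arm.

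The ITT main analysis is not affected, so the trial's main conclusion does not depend on this. The change should still be made, because the supportive tables cannot serve their purpose as defined.

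**What to change.** 1. Analyse fatal cases, intensive-care transfer, and non-invasive and mechanical ventilation in the ITT population only, and remove them from the PP analysis.
2. For the remaining criteria, replace the completers definition with one based on eligibility and absence of major protocol deviations up to the assessment concerned. A death after Visit 3 then no longer removes a patient from the Visit 3 analysis.
3. State that death, and cancellation of the drug under the ARDS and mechanical-ventilation rule, are outcomes and not deviations. These patients stay in PP as failures, by the same rule in both arms.

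This takes a few lines in the SAP, needs no new data and changes no clinical rule. The one downside is that the supportive PP result may be slightly less favourable to Areplivir.
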